7.11.2. EQ-5D-3L

Each of the 5 questions assessing mobility, self-care, usual activities, pain/discomfort, and anxiety/depression will be summarized by treatment group and by frequency distribution (profile) of the EQ-5D descriptive system ("No problems", "Some problems", "Extreme problems") at baseline, Week 4 and Week 8. Comparison between treatment groups at Week 8 will be performed utilizing the CMH test, controlling for strata: baseline EE status (present vs. not present), baseline heartburn severity level ($<3 \text{ vs.} \ge 3$) and the associate p-value will be reported. In addition, shift in response to each question from baseline to each visit postbaseline will be summarized using a shift table.

Change from baseline at week 4 and Week 8 in health state as assessed by a 0 to 100 visual analogue scale will be summarized by treatment group and analyzed using a similar MMRM approach described in Section 7.9.1.2.

8. **REFERENCES**

- 1. Statistical Considerations for Clinical Trials During the COVID-19 Public Health Emergency Guidance for Industry, U.S. Department of Health and Human Services Food and Drug Administration (June, 2020)
- 2. EuroQol G. EuroQol--a new facility for the measurement of health-related quality of life. The EuroQol Group. Health Policy. 1990; 16:199-208.
- 3. Newcombe, R. Interval estimation for the difference between independent proportions: Comparison of eleven methods. Stat. Med. 1 998; 17: 873-890.
- 4. Cohen, J. *Statistical power analysis for the behavioral sciences*, Hillsdale, NJ, Lawrence Earlbaum Associates. 1988
- 7. Rubin DB (1987) Multiple Imputation for Nonresponse in Surveys. John Wiley & Sons Ltd., New York.

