3.4. Assigning Patient to Treatment Group

Patients who meet all the inclusion criteria and none of the exclusion criteria will be randomized into the study at the Randomization Visit on Day 1. Approximately 550 patients will be stratified by 1) whether they have or do not have EE on the screening EGD and 2) their baseline heartburn severity level (<3 vs. \geq 3); and randomized through central randomization in a 1:1 ratio to either 1500-mg IW-3718 BID (while taking their usual label-dose PPI) or placebo BID (while taking their usual label-dose PPI).

The computer-generated randomization schedule was prepared by an independent statistician not otherwise associated with the study. Randomization numbers will be assigned by interactive web response system (IWRS).

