3.5. Blinding

This is a double-blind study. Ironwood Pharmaceuticals, Inc. (Ironwood, the Sponsor) study personnel, the site investigators, all other site study personnel, and the patient will remain blinded to individual patient treatment assignments throughout the study. Procedures for unblinding in the case of an emergency are included in Clinical Study Protocol C3718-301, Section 3.4.7.

4. **DETERMINATION OF SAMPLE SIZE**

The sample size of 660 patients (330 patients per treatment group) was chosen to ensure adequate power for using the fixed sequence testing method for the primary and key secondary efficacy parameters.

The power calculations for the primary and key secondary efficacy parameters are based on results from patients with evidence of pathological acid reflux (positive baseline Bravo status) in Study ICP-3718-202 that had a similar study population as the current study.

The primary efficacy parameter of the study is the Change from Baseline at Week 8 in Weekly Heartburn Severity Score (WHSS), and key secondary efficacy parameters include:

- Change from Baseline at Week 8 in Weekly Regurgitation Frequency Score (WRFS)
- Overall Heartburn Responder (OHR)
- Proportion of Heartburn-free Days during the 8-week Treatment Period (PHFD)

For definition of the efficacy parameters above, refer to Section 7.9.1.2 and Section 7.9.2.

Using data from patients in Study ICP-3718-202 with similar inclusion/exclusion criteria as the current study, ie, subjects with a positive baseline BRAVO status, we derived the estimated results at end of the study as follows:

Table 1:Study ICP-3718-202 - Summary of Efficacy Parameters at Week 8
(BRAVO+)

Order of Hypothesis Testing	Parameters	Placebo BID (+ PPIs)	1500 mg IW-3718 BID (+ PPIs)
1	Change from Baseline at Week 8 in WHSS	N = 43 Mean = -1.58 SD = 1.20	N = 51 Mean = -2.01 SD = 1.29
2	Change from Baseline at Week 8 in WRFS	N = 43 Mean = -0.81 SD = 1.12	N = 51 Mean = -1.26 SD = 0.91
3	Overall Heartburn Responder	18/49 = 36.7%	31/55 = 56.4%
4	Proportion of Heartburn-free Days during the 8-week Treatment Period	N = 48 Mean = 0.195 SD = 0.2822	N = 55 Mean = 0.268 SD = 0.2928

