5.3. Health Outcomes Assessments

WPAI-Sleep Disturbance-GERD

The Work Productivity and Activity Impairment Questionnaire: Sleep Disturbance-GERD (WPAI-Sleep-GERD) include questions about time lost from work, reduced productivity while at work, and reduced productivity while doing regular daily activities resulting from sleep disturbance due to GERD symptoms. Patients will complete the WPAI-Sleep-GERD at the Randomization Visit, the Week 4 Visit, and at the EOT Visit and will record their responses in the eDiary.

EQ-5D-3L

The EuroQol (EQ)-5D-3L is a generic measure of health widely used in Europe (2). The first component consists of 5 questions assessing the following dimensions: mobility, self-care, usual activities, pain/discomfort, and anxiety/depression. Responses to the 5 questions define a health state. The second component of the EQ-5D is a visual analogue scale, asking patients to rate their health from 0 to 100 (0 represents worst imaginable health state and 100 represents best imaginable health state). Patients will complete the EQ-5D-3L at the Randomization Visit, the Week 4 Visit, and at the EOT Visit and will record their responses in the eDiary.

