6. STATISTICAL METHODS

6.1. General Methods

In general, descriptive statistics will be presented by treatment group and by visit, as applicable. Descriptive statistics including the number of patients, mean, standard deviation (SD), median, minimum, and maximum will be calculated for continuous variables. Frequencies and percentages for each category will be calculated for categorical variables. All hypothesis tests will be 2-sided with a 5% significance level, and 95% confidence intervals (CIs) will be used.

Baseline EE status (EE vs. non-EE) that is based on local reader's assessments using images created during a screening EGD, and baseline WHSS (<3 vs. ≥3) per eDiary assessments by mRESQ-ed questionnaire are used for analysis, whenever it is appropriate.

All statistical analyses will be performed using SAS Version 9.4 (or later).

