6.2. Adjusting for Baseline Characteristics and Covariates

Analyses of efficacy parameters will be adjusted by randomization stratification variables baseline EE status (EE vs. non-EE) and baseline WHSS ($\leq 3 \text{ vs.} \geq 3$).

As a general approach, the baseline value will be included in the linear mixed effects-model for repeated measures (MMRM) and Poisson model analysis as a covariate when the postbaseline or change from baseline values are analyzed, and the randomization stratification variables baseline EE status and baseline WHSS ($<3 \text{ vs.} \geq 3$) will be adjusted in the analysis model as well. Heterogeneity of slopes will be explored, when appropriate.

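### The Week 8 tests of the five EQ-5D-3L items leave out the patient's baseline answer, which costs some precision and leaves them sensitive to chance baseline imbalance

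*SAP*

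**What the plan says.** SAP Section 7.11.2 summarises the five three-level EQ-5D-3L items at baseline, Week 4 and Week 8. It then sets the between-group test: "Comparison between treatment groups at Week 8 will be performed utilizing the CMH test, controlling for strata: baseline EE status", together with baseline heartburn severity (<3 vs ≥3), and commits to reporting the p-value. The section does not say which CMH statistic applies to a three-level ordered response.

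The baseline answers exist. SAP Section 5.3 states: "Patients will complete the EQ-5D-3L at the Randomization Visit, the Week 4 Visit, and at the EOT Visit". For the five items they are used only in the frequency summary and in this display: "shift in response to each question from baseline to each visit postbaseline will be summarized using a shift table".

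The other half of the questionnaire is handled differently. "Change from baseline at week 4 and Week 8 in health state as assessed by a 0 to 100 visual analogue scale" is analysed by an MMRM like that of Section 7.9.1.2, which carries the baseline value as a covariate. Section 7.11.1 does the same for the WPAI measures. The general rule in Section 6.2 is that "the baseline value will be included in the linear mixed effects-model for repeated measures (MMRM) and Poisson model analysis as a covariate". CMH tests are not named in that sentence.

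**The concern.** A patient's answer on mobility or anxiety at Week 8 is likely to resemble the answer given at randomisation. Neither EE status nor heartburn severity is a close stand-in for it. A test that omits a predictive baseline value works with more residual variation than it needs to. Its statistic also shifts with whatever difference the arms happened to have on that item at the start. At stake are five reported p-values that are less precise, and in an unluckily imbalanced trial less easy to interpret, than the collected data allow.

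**Working it through.** **Plan's own figure.** There is none to reproduce. The documents give no power, effect size, item frequency or baseline-to-Week 8 correlation for the EQ-5D-3L. The size below therefore rests on stated assumptions, varied over a range.

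**Inputs from the SAP.**
- Strata: EE status by heartburn severity, so 2 × 2 = 4 (Section 7.11.2).
- Allocation 1:1 (Section 3.4).
- Level: "All hypothesis tests will be 2-sided with a 5% significance level" (Section 6.1).
- Size: Section 3.4 has "Approximately 550 patients will be stratified by" EE status and heartburn severity, while Section 4 is built on 330 per group, 660 in all. The main runs use 550.

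**Assumed inputs.**
- Baseline and Week 8 latent scores are bivariate normal with correlation 0.4, 0.6 or 0.8, cut to three levels.
- Item frequencies (no / some / extreme problems) are 40/55/5%, 70/28/2% or 95/4.5/0.5%.
- The treatment shift is 0.2 SD, or 0.38 SD for the near-ceiling item.

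**Statistic.** Row mean scores. In stratum k, with n_k patients split n_1k and n_0k, item scores y and stratum mean ȳ_k:

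Z = Σ_k (sum of y on IW-3718 − n_1k·ȳ_k) / √V, where V = Σ_k [n_1k·n_0k / (n_k(n_k − 1))]·Σ(y − ȳ_k)².

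The planned test uses 4 strata. The alternative crosses them with baseline no problems vs some/extreme problems, giving 4 × 2 = 8. Both sides use the same statistic, so the difference is due to the extra stratum alone.

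**Power at 550 patients.**

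| Assumed item | Planned (corr. 0.4/0.6/0.8) | With baseline stratum | Gain, points |
|---|---|---|---|
| 40/55/5% | 51/50/48% | 54/58/66% | 3/8/18 |
| 70/28/2% | 45/42/43% | 47/50/58% | 2/8/15 |
| 95/4.5/0.5% | 44/44/45% | 44/44/49% | 0/0/4 |

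The gains are differences of the rounded figures. The planned power should not depend on the correlation, so the spread of 48 to 51% in the first row is simulation noise. Two further runs of that row gave 51/51/52% rising to 54/58/67%, and 50/52/50% rising to 54/60/66%. At correlation 0.8 the gain is therefore better read as 15 to 18 points (67 − 52 = 15; 66 − 48 = 18). At 660 patients the same item went from 59/58/59% to 62/68/75%.

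**Validity.** Simulated type I error for the two-level version was 4.3 to 6.0%, in line with a nominal 5%.

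**Chance imbalance.** A separate set of runs used correlations 0.3, 0.5 and 0.7, a 40/55/5% item, 550 and 660 patients, and all three baseline levels as strata. Overall type I error was 0.046 to 0.056 with or without adjustment. In the 10% of null trials with the largest baseline difference on the item, the planned test rejected in about 0.08–0.09, 0.11–0.13 and 0.18–0.20 of cases. The correlation between its statistic and the baseline difference was about 0.23, 0.38 and 0.53. With the baseline strata it was about 0. That last result is for three levels and was not recomputed for two.

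**The case against.** The strongest reply is that nothing here is an error. Section 6.2 confines baseline-value adjustment to MMRM and Poisson models and separately asks for the stratification variables. Section 7.11.2 does what that rule says. This stands: a reader might infer a breach of the SAP's own rule, and the text does not support that reading.

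A reader might also infer that the p-values are biased. They are not. Allocation is randomised 1:1 and overall type I error stays near 5%. The dependence on baseline is conditional on a chance imbalance, and the planned baseline frequencies and shift tables would make such an imbalance visible. Neither display adjusts the p-value.

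Nor are the EQ-5D items the only baseline-measured outcome left unadjusted, as the contrast with the visual analogue scale might suggest. In SAP Table 7 the analysis of EE improvement by at least one grade also uses CMH, and no baseline-grade stratum is named. The EQ-5D test follows the SAP's general CMH convention.

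Finally, the benefit is uneven. Where nearly everyone reports no problems, the gain is nil unless the correlation is high, and some of the five items may behave that way. This also stands, and the table shows it.

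**Conclusion.** The point holds as a minor improvement in efficiency. The planned CMH tests are valid, but they set aside a predictor that is already collected, while the visual analogue scale completed at the same visits is baseline-adjusted. At 550 patients the loss is about 2 to 3 points of power at latent correlation 0.4, about 8 at 0.6 and about 15 to 18 at 0.8 for items with reasonable spread. For a near-ceiling item it is 0 to 4 points. These sizes depend wholly on assumed correlations, frequencies and effects. The EQ-5D-3L is outside the fixed sequence of SAP Section 6.6 and no power claim rests on it, so no primary or key secondary conclusion changes.

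**What to change.** In SAP Section 7.11.2, specify a CMH row-mean-scores test stratified by EE status, heartburn severity and the baseline response to the same item, coded as no problems, some or extreme problems, or missing. Collapsing the upper two levels avoids sparse cells. Naming the statistic also settles which p-value is to be reported for an ordered response; that part is a clarification, and its effect was not quantified.

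The cost is one sentence and one extra stratification factor, with no new data. It should be settled before unblinding.

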Appendix 1.Missing Data Simulation to Support the Key Efficacy
Parameters Scoring Algorithm

A missing data simulation study was conducted to assess the impact of the missing data on the scoring algorithm of the key efficacy parameters. The following assumptions were made for the simulation:

- Patients with evidence of pathological acid reflux (positive Bravo status) at baseline in Study ICP-3718-202 represent a study population that is similar to the current study population.
- The efficacy parameters WHSS, WRFS and PHFD in the current study follow the same underlying data distribution as in Study ICP-3718-202.

In Study ICP-3718-202, 45 patients with a positive Bravo status at baseline had non-missing daily assessments in the placebo and IW-3718 1500 mg BID groups combined. The daily assessments were used to derive the efficacy parameters WHSS, WRFS and PHFD. These 45 patients were used for the simulation study.

In Study ICP-3718-202, approximately 10% of patients prematurely discontinued from the study. In the initial simulation, it was assumed that 10% of patients had a given number of missing daily data at each week (ie, the missing data rate). In a second simulation, it was assumed that 20% of patients had a given number of missing daily data at each week.

Daily Scores

Derivation of PHFD is based on Item #1 of mRESQ-eD (Appendix 5). The simulations were run on the value of Item #1.

The daily score that is used to derive the WHSS is the greater score of Item #1 and Item #2 of the mRESQ-eD, which both assess heartburn severity for a given day.

Similar to the WHSS, the daily score that is used to derive the WRFS is the greater score of Item #6 and Item #7 of the mRESQ-ed, which both assess regurgitation frequency for a given day.

It was assumed that a scenario whereby a patient misses 1 of the 2 mRESQ-eD items does not occur. The reason is that when a patient answers a mRESQ-eD question, the next question automatically appears on the device, and it cues the patient to answer that question. Given the nature of the device, there are most likely only 2 scenarios for the mRESQ-eD data collection: 1) a patient answers all mRESQ-eD items; 2) none of the items are answered. The experience of Study ICP-3718-202 supports this. There was no instance where the eDiary had partial data for a given day. Similarly, this has been the experience in the 2 ongoing Phase 3 studies.

Based on the above discussions, the simulations conducted for WHSS and WRFS began with the daily scores, rather than the item scores. The WHSS and WRFS are calculated as the weekly average of the non-missing daily scores.

Weekly Heartburn Severity Score and Weekly Regurgitation Frequency Score

For the weekly scoring algorithm, a minimum number of non-missing daily scores over the 7-day period should be required to calculate the weekly scores. In the simulation study, we randomly replaced non-missing daily scores with missing daily scores for an increasing number

of days, beginning with 1 day and proceeding up to 6 days. We also ran the simulations with 2 different percentages of patients with missing data at each week, 10% and 20%.

A patient cluster is defined as all patient daily scores with a weekly repeated measures structure. Given the sample size of the current study, approximately 550 patients, and a patient cluster bootstrapping resampling based on Study ICP-3718-202 subset that includes 45 patients, we performed the following steps for the simulation:

- 1. A bootstrapping resampling process with replacement to select 550 patient clusters with 2000 replications was applied.
- 2. In each replicated dataset, a given percentage (eg, 10% or 20%) of patient clusters was randomly selected.
- 3. In each replicated dataset, in each patient cluster that was selected for in Step 2, at each week, a given number of daily scores (ie, 4, 5, or 6 days) was randomly selected and set to missing. (Each patient has a planned 8 weeks of data assessments and at each week there are 7 planned daily scores.)
- 4. Average change from baseline by week was calculated for both non-missing and missing data, respectively.

Across all replicated datasets, for both the data without any missing daily scores and the data replaced by daily missing scores, their resultant weekly average score, median, and standard deviation were calculated. Comparing the summary scores between these 2 data conditions helped us determine the minimum number of non-missing daily scores that should be included in the efficacy parameter scoring algorithms.

The summary statistics for the efficacy parameter WHSS are presented in Table 11. The descriptive summary statistics were calculated for both the non-missing daily score data and the missing daily score data, by the number of days with missing data (ie, 4, 5, or 6 days). The data were compared using ratios.

The comparisons show that the means, medians, and standard deviations are almost the same for the non-missing and missing data, across the different combinations of overall missing rate and number of daily scores missing. Specifically, for the extreme case of 20% of patient clusters with 6 daily scores missing in each week, the weekly average change from baseline compared to the non-missing data shows that the means, medians, and standard deviations are almost the same. Given this finding, the results suggest that, for the current study, even if a patient has only 1 valid daily score within a week, it still can be used to represent the average for the week, to generate a robust analysis result. The summary is based on a total of 2000 replicated datasets, and for each of the replicated datasets the number of patients is 550.

XX7 I-	Non-Missing				With I	Missing	Ratio			
Week				10% M	lissing in Ea	ch Replicat	(With Missing/Non-missing)			
	Mean	Median	SD	Missing ^a	Mean	Median	SD	Mean	median	SD
1	-0.69	-0.7	1.04	4	-0.69	-0.7	1.05	1	1	1.01
2	-1.14	-1.1	1.13		-1.14	-1.1	1.14	1	1	1.01
3	-1.36	-1.3	1.18		-1.36	-1.3	1.19	1	1	1.01
4	-1.62	-1.7	1.24		-1.62	-1.7	1.25	1	1	1.01
5	-1.75	-1.7	1.30		-1.75	-1.7	1.31	1	1	1.01
6	-1.84	-1.9	1.22		-1.84	-1.9	1.23	1	1	1.01
7	-1.84	-2.0	1.29		-1.84	-2.0	1.30	1	1	1.01
8	-1.91	-1.9	1.34		-1.91	-1.9	1.35	1	1	1.01
1	-0.69	-0.7	1.04	5	-0.69	-0.7	1.07	1	1	1.03
2	-1.14	-1.1	1.13		-1.14	-1.1	1.15	1	1	1.02
3	-1.36	-1.3	1.18		-1.36	-1.3	1.20	1	1	1.02
4	-1.62	-1.7	1.24		-1.62	-1.7	1.26	1	1	1.02
5	-1.75	-1.7	1.30		-1.75	-1.7	1.32	1	1	1.01
6	-1.84	-1.9	1.22		-1.84	-1.9	1.24	1	1	1.02
7	-1.84	-2.0	1.29		-1.84	-2.0	1.31	1	1	1.01
8	-1.91	-1.9	1.34		-1.91	-1.9	1.36	1	1	1.01
1	-0.69	-0.7	1.04	6	-0.69	-0.7	1.10	1	1	1.06
2	-1.14	-1.1	1.13		-1.14	-1.1	1.18	1	1	1.05
3	-1.36	-1.3	1.18		-1.36	-1.3	1.23	1	1	1.04
4	-1.62	-1.7	1.24		-1.62	-1.7	1.28	1	1	1.04
5	-1.75	-1.7	1.30		-1.75	-1.7	1.34	1	1	1.03
6	-1.84	-1.9	1.22		-1.84	-1.9	1.26	1	1	1.04
7	-1.84	-2.0	1.29		-1.84	-2.0	1.33	1	1	1.03
8	-1.91	-1.9	1.34		-1.91	-2.0	1.38	1	1	1.03
		1	1	20% N	Aissing in Ea	ch Replicate	d Data			1
1	-0.69	-0.7	1.04	4	-0.69	-0.7	1.07	1	1	1.03
2	-1.14	-1.1	1.13		-1.14	-1.1	1.16	1	1	1.02
3	-1.36	-1.3	1.18		-1.36	-1.3	1.20	1	1	1.02
4	-1.62	-1.7	1.24		-1.62	-1.6	1.26	1	1	1.02
5	-1.75	-1.7	1.30		-1.75	-1.7	1.32	1	1	1.01
6	-1.84	-1.9	1.22		-1.84	-1.9	1.24	1	1	1.02
7	-1.84	-2.0	1.29		-1.84	-2.0	1.31	1	1	1.01
8	-1.91	-1.9	1.34		-1.91	-1.9	1.36	1	1	1.01
1	-0.69	-0.7	1.04	5	-0.69	-0.6	1.09	1	0.9	1.05
2	-1.14	-1.1	1.13		-1.14	-1.1	1.18	1	0.9	1.04

 Table 11:
 Simulation Results for WHSS During the 8-week Treatment Period

Week		Jon Missin	ä		With N	Aissing	Ratio			
week	Г	Non-Missin	g	10% M	lissing in Ea	ch Replicat	ed Data	(With Missing/Non-missi		
	Mean	Median	SD	Missing ^a	Mean	Median	SD	Mean	median	SD
3	-1.36	-1.3	1.18		-1.36	-1.3	1.22	1	1	1.04
4	-1.62	-1.7	1.24		-1.62	-1.6	1.28	1	1	1.03
5	-1.75	-1.7	1.30		-1.75	-1.7	1.34	1	1	1.03
6	-1.84	-1.9	1.22		-1.84	-1.9	1.25	1	1	1.03
7	-1.84	-2.0	1.29		-1.84	-2.0	1.33	1	1	1.03
8	-1.91	-1.9	1.34		-1.91	-2.0	1.38	1	1	1.02
1	-0.69	-0.7	1.04	6	-0.69	-0.7	1.16	1	1	1.12
2	-1.14	-1.1	1.13		-1.14	-1.1	1.23	1	0.9	1.09
3	-1.36	-1.3	1.18		-1.36	-1.3	1.28	1	1	1.08
4	-1.62	-1.7	1.24		-1.62	-1.7	1.33	1	1	1.07
5	-1.75	-1.7	1.30		-1.75	-1.7	1.38	1	1	1.06
6	-1.84	-1.9	1.22		-1.84	-2.0	1.30	1	1	1.07
7	-1.84	-2.0	1.29		-1.84	-2.0	1.37	1	1	1.06
8	-1.91	-1.9	1.34		-1.91	-2.0	1.42	1	1	1.06

a. Number of daily scores missing.

Table 12 shows summary results for the WRFS. These results show a similar pattern to that observed for WHSS and a similar conclusion can be drawn. That is, for the current study setting, the WRFS data are robust, and 1 daily score can be used to represent a weekly average value for data analysis. The summary is based on a total of 2000 replicated datasets, and for each of the replicated datasets the number of patients is 550.

Week	Non-Missing				With N	Aissing	Ratio			
week	1	NUII-IVIISSIII	g	10% M	issing in Ea	(With Missing/Non-missing				
	Mean	Median	SD	Missing ^a	Mean	Median	SD	Mean	median	SD
1	-0.43	-0.3	0.76	4	-0.43	-0.3	0.77	1	1	1.02
2	-0.78	-0.7	0.93		-0.78	-0.7	0.94	1	1	1.01
3	-0.78	-0.7	1.02		-0.78	-0.7	1.03	1	1	1.01
4	-0.96	-0.8	1.06		-0.96	-0.8	1.06	1	1	1.01
5	-0.98	-0.8	1.06		-0.97	-0.8	1.07	1	1	1.01
6	-0.95	-0.9	1.00		-0.95	-0.9	1.01	1	1	1.01
7	-0.96	-0.9	1.04		-0.96	-0.9	1.05	1	1	1.01
8	-1.07	-1.1	1.11		-1.07	-1.1	1.12	1	1	1.01
1	-0.43	-0.3	0.76	5	-0.43	-0.3	0.78	1	1	1.03
2	-0.78	-0.7	0.93		-0.78	-0.7	0.95	1	1	1.02
3	-0.78	-0.7	1.02		-0.78	-0.7	1.04	1	1	1.02
4	-0.96	-0.8	1.06		-0.96	-0.8	1.07	1	1	1.01
5	-0.98	-0.8	1.06		-0.97	-0.8	1.07	1	1	1.01

 Table 12:
 Simulation Results for WRFS During the 8-week Treatment Period

Weels		Jon Missin	~		With N	Aissing	Ratio			
Week	Γ	Non-Missin	g	10% M	lissing in Ea	ch Replicat	ed Data	(With Missing/Non-missin		
	Mean	Median	SD	Missing ^a	Mean	Median	SD	Mean	median	SD
6	-0.95	-0.9	1.00		-0.95	-0.9	1.02	1	1	1.01
7	-0.96	-0.9	1.04		-0.96	-0.9	1.06	1	1	1.01
8	-1.07	-1.1	1.11		-1.07	-1.1	1.13	1	1	1.01
1	-0.43	-0.3	0.76	6	-0.43	-0.3	0.81	1	1	1.07
2	-0.78	-0.7	0.93		-0.78	-0.7	0.97	1	1	1.04
3	-0.78	-0.7	1.02		-0.78	-0.7	1.06	1	1	1.04
4	-0.96	-0.8	1.06		-0.96	-0.8	1.09	1	1	1.03
5	-0.98	-0.8	1.06		-0.98	-0.8	1.09	1	1.1	1.03
6	-0.95	-0.9	1.00		-0.95	-0.9	1.04	1	1	1.03
7	-0.96	-0.9	1.04		-0.96	-0.9	1.07	1	1	1.03
8	-1.07	-1.1	1.11		-1.07	-1.1	1.14	1	1	1.03
				20% N	Aissing in Ea	ch Replicate	d Data			
1	-0.43	-0.3	0.76	4	-0.43	-0.3	0.78	1	1.1	1.03
2	-0.78	-0.7	0.93		-0.78	-0.7	0.95	1	1	1.02
3	-0.78	-0.7	1.02		-0.78	-0.7	1.04	1	1	1.02
4	-0.96	-0.8	1.06		-0.96	-0.8	1.07	1	1	1.01
5	-0.98	-0.8	1.06		-0.98	-0.8	1.07	1	1	1.01
6	-0.95	-0.9	1.00		-0.95	-0.9	1.02	1	1	1.02
7	-0.96	-0.9	1.04		-0.96	-0.9	1.06	1	1	1.01
8	-1.07	-1.1	1.11		-1.07	-1.1	1.13	1	1	1.01
1	-0.43	-0.3	0.76	5	-0.43	-0.3	0.81	1	1.1	1.06
2	-0.78	-0.7	0.93		-0.78	-0.7	0.97	1	1	1.03
3	-0.78	-0.7	1.02		-0.78	-0.7	1.05	1	1	1.03
4	-0.96	-0.8	1.06		-0.96	-0.8	1.08	1	1	1.03
5	-0.98	-0.8	1.06		-0.97	-0.8	1.09	1	1.1	1.03
6	-0.95	-0.9	1.00		-0.95	-0.9	1.03	1	1	1.03
7	-0.96	-0.9	1.04		-0.96	-0.9	1.07	1	1	1.03
8	-1.07	-1.1	1.11		-1.07	-1.1	1.14	1	1	1.02
1	-0.43	-0.3	0.76	6	-0.43	-0.3	0.87	1	0.9	1.14
2	-0.78	-0.7	0.93		-0.78	-0.7	1.01	1	1	1.08
3	-0.78	-0.7	1.02		-0.78	-0.7	1.10	1	1	1.07
4	-0.96	-0.8	1.06		-0.96	-0.9	1.12	1	1.1	1.06
5	-0.98	-0.8	1.06		-0.97	-0.9	1.13	1	1.1	1.06
6	-0.95	-0.9	1.00		-0.95	-0.9	1.07	1	1.1	1.07
7	-0.96	-0.9	1.04		-0.96	-1.0	1.11	1	1	1.06
8	-1.07	-1.1	1.11		-1.07	-1.1	1.18	1	0.9	1.06

a. Number of daily scores missing.

Proportion of Heartburn-free Days During the 8-week Treatment Period

A similar bootstrapping resampling process for patient clusters that was used for the parameters WHSS and WRFS can be applied to PHFD. The descriptive summary statistics were calculated for both the non-missing daily score data and the missing daily score data, by the number of days with missing data (ie, 4, 5, or 6 days). The results are presented in Table 13.

The comparisons show that the means, medians, and standard deviations are almost the same for the non-missing and missing data, across different combinations of overall missing rate and number of daily scores missing. This suggests that the algorithm for calculating the PHFD (the number of heartburn-free days divided by the number of diary entry days) is robust. The summary is based on a total of 2000 replicated datasets, and for each of the replicated datasets the number of patients is 550.

Non-Missing		With Missing				Ratio			
	NOII-1V1155111	g	10% Missing in Each Replicated Data				(With Missing/Non-missing)		
Mean	Median	SD	Missing ^a	Mean	Median	SD	Mean	median	SD
0.307	0.2	0.315	4	0.307	0.2	0.315	1	1	1
0.307	0.2	0.315	5	0.308	0.2	0.315	1	1	1
0.307	0.2	0.315	6	0.307	0.2	0.316	1	1	1
			20% N	/lissing in Ea	ch Replicate	d Data			
0.307	0.2	0.315	4	0.307	0.2	0.315	1	1	1
0.307	0.2	0.315	5	0.308	0.2	0.316	1	1	1
0.307	0.2	0.315	6	0.308	0.2	0.317	1	1	1.01

Table 13: Simulation Results for PHFD During the 8-week Treatment Period

a. Number of daily scores missing.

